9.3 Randomization and Participant Numbering

Every potential participant who is prescreened by telephone according to the IRB-approved script will be assigned a seven-character alphanumeric Screening Number and recorded on the Screening Log. This number will begin with 'S5' to identify that it is a Screening Number. The next two digits represent the site number (e.g., '11'), followed by a three-digit screening identifier starting with '501'. The screening identifier will be assigned to each prescreened participant at a site sequentially. For example, the first Screening Number at Site 11 will be S511501 and first Screening Number at Site 12 will be S512501.

Each participant who passes Screening and is enrolled in the trial at Visit 0 will be assigned a seven-digit Participant Number. The first two digits will be '11'. The next two digits represent the site number (e.g., '11'), followed by a three-digit participant identifier starting with '001'. The Participant Number will be assigned to each enrolled participant at a site sequentially. For example, the first Participant Number at Site 12 will be 1112001. Eligible participants will be enrolled in the study and sequentially assigned an identification number. All participants will also be assigned a unique participant identifier within the database for use in analysis.

Participants will be randomized in 1:1 allocation in a blinded fashion to the MDMA-assisted psychotherapy group and the placebo plus psychotherapy group, stratified by clinical site. Randomization will be managed via an Interactive Web Randomization System (IWRS) based on

a centralized randomization schedule developed by an independent third-party vendor to maintain blinding.

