14.1 Power and Sample Size Determination

The statistical power calculations were made by fitting an MMRM model to CAPS-4 data from the Phase 2 study MP1 to obtain covariance parameter estimates. The Phase 2 MP1 study had a similar design with primary outcomes measured by change in CAPS-4 outcome scores, which allowed for estimation of within-subject covariance parameters. The following inputs created the 90% statistical power estimate using the PASS 14 Mixed Models Repeated Measures module:

- a. N=47 per group (allowing for 3 dropouts per treatment group)
- b. Alpha=0.0499
- c. 1000 simulations
- d. Change from Baseline means of 5.5, 12.8, and 20.5 for placebo. Change from Baseline means of 17.2, 31.1, and 37.4, for MDMA at visits 1, 2, and 3, respectively
- e. Two levels of treatment factor (MDMA, Placebo)
- f. Three within subject levels (3 treatment visits)
- g. Subject level variance=335
- h. Variance of R (diagonal elements)=280
- i. Rho=0.5
- j. Unstructured covariance

Additional participants may be added to the sample size at the recommendation of the Data Monitoring Committee (DMC) from the results of an administrative interim analysis ([Section 14.2.3](#)) occurring after 60% of the mITT participants have completed a final assessment of the Primary Outcome (Visit 19) and terminated treatment.

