7.0 Sample Size and Power Considerations

The statistical power calculations were made by fitting an MMRM model to CAPS-4 data from the Phase 2 study MPI data to obtain covariance parameter estimates. CAPS-4 data was also converted to the CAPS-5 scale, by dividing the CAPS-4 score by 34 and multiplying by 20 to obtain the CAPS-5 score, and both methods came up with the same level of statistical power. The following inputs created the 90% statistical power estimate using the PASS 14 Mixed Models Repeated Measures module.

- a. N=47 per group (allowing for 3 dropouts per treatment group)
- b. Alpha = 0.0499
- c. 1000 simulations
- d. Change from baseline means of 5.5, 12.8, and 20.5 for placebo. Change from baseline means of 17.2, 31.1, and 37.4, for MDMA at visits 1, 2, and 3, respectively
- e. Two levels of treatment factor (MDMA, Placebo)
- f. Three within subject levels (3 treatment visits)
- g. Subject level variance = 335
- h. Variance of R (diagonal elements) = 280
- i. Rho = 0.5
- j. Unstructured covariance

Additional participants may be added to the sample size at the recommendation of the Data Monitoring Committee (DMC) from the results of an administrative interim analysis (Section 8.9) occurring after 60% of the *mITT* participants have completed a final assessment of the Primary Outcome (Visit 19) and terminated treatment.

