8.7.1 Primary Efficacy Analyses

The *de jure* estimand of treatment efficacy will be used to estimate the causal effect of MDMA-assisted psychotherapy on PTSD symptom severity in the intended population of patients with PTSD from any cause (Estimand 1 in Table 4). All efficacy analyses will be based on the *mITT* analysis set. The primary treatment comparison will be made at a 2-sided, 0.0499 level of alpha. The primary estimator of effects of initially randomized treatments will be the difference between groups in mean change in CAPS-5 Total Severity Scores from Baseline to 18 weeks after randomization (Visit 19). Least squares means from a restricted maximum likelihood (REML)-based mixed model for repeated measures (MMRM) will be used to compare treatment groups at Visit 19. CAPS-5 data collected after treatment discontinuation will not be included in the *de jure* estimand. Missing data will not be imputed. The model is specified as follows: Let Y_{ij} be the change in the CAPS-5 score from the i th participant at the j th visit, $i = 1, \dots, n$ and $j = 1, 2, 3$, corresponding to post-baseline visits 8, 13, and 19, respectively. The treatment variable X_i is the randomized treatment of the i th participant. The variables T_1 and T_2 , are variables indicating if the data from that record are from visit 13, or 19, respectively. Covariates included in the MMRM model are the continuous baseline CAPS-5 Total Severity Score and the binary variable indicating dissociative subtype at baseline. Investigative site is included as a fixed effect. The regression model is specified as follows:

$$Y_{ij} = \alpha + \beta_1 X_i + \beta_{21} T_1 I(j=2) + \beta_{22} T_2 I(j=3) + \beta_{31} T_1 X_i I(j=2) + \beta_{32} T_2 X_i I(j=3) + \beta_4 \text{Baseline_CAPS}_i + \beta_5 \text{DS}_i + \phi \text{Site}_i + \varepsilon_{ij}$$

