8.9 Administrative Interim Analysis

An unblinded administrative interim analysis is planned to be performed at a single time point after the first 60% of participants in the *mITT* set have completed the final CAPS-5 follow-up assessment and terminated treatment, including early termination participants who have

completed their final CAPS-5, and 100 participants have been enrolled. The objective of the administrative interim analysis is to conduct a sample size re-estimation. The key secondary endpoint will not be evaluated at the interim analysis. The detailed results of the interim analysis will not be revealed to the site staff, participants, IRs, or sponsor staff/designees except for a single designated sponsor representative from MAPS. The independent DMC statistician will perform the unblinded administrative interim analysis as described in the DMC Charter. In addition, procedures will be developed to ensure the blinding of the participant level data for parties outside of the Independent Statistical Group (ISG).

Sample size re-estimation: Based on the result of calculating conditional power using the estimated effect size from the first 60% of participants in the *mITT* set, the sample size may be increased. The table below shows the range of possible effect sizes that could be observed at the interim analysis and what the guidance from the DMC could be for the adjusted sample size.

Table 6: Observed Effect Sizes and Corresponding Sample Size for 90% Conditional Power Guidance at the Interim Analysis (N=60)

Effect Size	≤ 0.32	0.32	0.34	0.36	0.38	0.40	0.42	0.44
Mean Change	-	5.76	6.12	6.48	6.84	7.2	7.56	7.92
Conditional Power ^[1]	< 50%	52%	60%	67%	74%	80%	85%	89%
Increase in Sample Size to Restore 90% Conditional Power	No increase	240	180	140	110	70	40	10

[1] Conditional Power based on the alternative hypothesis effect size as observed in the first 60 subjects.

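### SAP 7.0 and Table 6 do not rest on one SD (14.6 CAPS-5 points against 18.0), and at 60 of 100 the printed effect sizes do not give the printed conditional powers

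*SAP*

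**What the plan says.** Protocol 14.1 and SAP 7.0 list the same power inputs. The Protocol gives their source: "The statistical power calculations were made by fitting an MMRM model to CAPS-4 data from the Phase 2 study MP1 to obtain covariance parameter estimates". These inputs are:

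- "N=47 per group (allowing for 3 dropouts per treatment group");
- alpha 0.0499, with SAP 8.7.1 confirming the sidedness: "The primary treatment comparison will be made at a 2-sided, 0.0499 level of alpha";
- "Change from baseline means of 5.5, 12.8, and 20.5 for placebo", and "Change from baseline means of 17.2, 31.1, and 37.4, for MDMA at visits 1, 2, and 3, respectively";
- subject variance 335, residual variance 280, rho 0.5.

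SAP 7.0 adds that CAPS-4 was converted to CAPS-5 by dividing by 34 and multiplying by 20, and that "both methods came up with the same level of statistical power".

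SAP 8.9 then gives Table 6, "Observed Effect Sizes and Corresponding Sample Size for 90% Conditional Power Guidance at the Interim Analysis (N=60"). Its rows are effect size (0.32 to 0.44), mean change (5.76 to 7.92), conditional power (52% to 89%) and the increase needed to restore 90% (240 down to 10). The footnote bases conditional power on the effect observed in the first 60 participants. The text below the table says that type I error is preserved because the smallest effect size leading to an increase has conditional power above 50%. Neither section prints an SD, and Table 6 does not name the scale of its mean change row.

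**The concern.** Table 6 is the only place where the SAP sets a difference beside its standardised effect size, so it reveals an SD. That SD is not the one behind the 90% power, on either scale. The SAP gives no independent support for the CAPS-5 SD: the agreement between the two scales holds for any SD, because power depends only on the ratio of difference to SD and a common multiplier cancels.

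Two things are at stake. First, a DMC reading Table 6 would get different guidance from different rows. Second, the SAP's type I error argument relies on the 50% boundary sitting where the effect size row puts it.

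**Working it through.** **1. Reproduce the stated power.** Visit-3 difference: 37.4 − 20.5 = 16.9. SD: √(335 + 280) = √615 = 24.80. Standardised difference: 16.9/24.80 = 0.681. With 47 per group (1:1) and two-sided alpha 0.0499 (z = 1.961):

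- normal formula: Φ(0.681 × √(47/2) − 1.961) = Φ(1.343) = 91.0%;
- noncentral t: 90.5%;
- simulation of the visit-3 contrast with the stated covariance: 90.3%.

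The 90% reproduces.

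**2. Convert to CAPS-5.** Difference: 16.9 × 20/34 = 9.94. SD: 24.80 × 20/34 = 14.59. The ratio is still 0.681, so power is unchanged, as it must be.

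**3. SD implied by Table 6.** 5.76/0.32 = 6.12/0.34 = 6.48/0.36 = 6.84/0.38 = 7.2/0.40 = 7.56/0.42 = 7.92/0.44 = 18.0. This is neither 14.59 nor 24.80.

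**4. Conditional power at the stated design.** With n = 60, N = 100 and θ = difference/SD,

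CP = Φ((θ√(N/4) − z)/√(1 − n/N)) = Φ((5θ − 1.961)/0.632).

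First column, printed effect size: θ = 0.32 gives Φ(−0.571) = 28%. First column, mean change with SD 14.59: θ = 5.76/14.59 = 0.395 gives Φ(0.021) = 51%. All columns:

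| Printed effect size | Printed mean change | Printed CP | CP from printed effect size | CP from mean change, SD 14.59 | Effect size at SD 14.59 |
|---|---|---|---|---|---|
| 0.32 | 5.76 | 52% | 28% | 51% | 0.39 |
| 0.34 | 6.12 | 60% | 34% | 59% | 0.42 |
| 0.36 | 6.48 | 67% | 40% | 66% | 0.44 |
| 0.38 | 6.84 | 74% | 46% | 73% | 0.47 |
| 0.40 | 7.2 | 80% | 52% | 79% | 0.49 |
| 0.42 | 7.56 | 85% | 59% | 84% | 0.52 |
| 0.44 | 7.92 | 89% | 65% | 88% | 0.54 |

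Solving each column for the SD that makes its mean change give the printed conditional power yields 14.43 to 14.47. The 50% boundary is at θ = 1.961/5 = 0.392, which is 5.72 points at SD 14.59; it is not at 0.32.

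**5. The increase row.** The same formula with N = 100 + increase and n = 60:

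| Mean change | Printed increase | CP reached, SD 14.59 | Increase for 90%, SD 14.59 | CP reached, printed effect size | Increase for 90%, printed effect size |
|---|---|---|---|---|---|
| 5.76 | 240 | 97% | 142 | 86% | 285 |
| 6.12 | 180 | 96% | 111 | 84% | 237 |
| 6.48 | 140 | 96% | 84 | 83% | 198 |
| 6.84 | 110 | 95% or 96% | 61 | 83% | 164 |
| 7.2 | 70 | 94% | 41 | 79% | 135 |
| 7.56 | 40 | 93% | 24 | 76% | 110 |
| 7.92 | 10 | 91% | 7 | 70% | 88 |

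Neither SD returns 90% with the printed increases.

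**6. Reading by row.** At SD 14.59, an observed 5.76 points is an effect size of 0.395. The mean change row says add 240; the nearest effect size column (0.40) says add 70.

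**7. What-if: SD 18 in the power calculation.** Difference 9.94, 47 per group: 75.4% (noncentral t; 76.3% by the normal formula). With 50 per group: 78.0%. For 90%: about 70 per group.

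**The case against.** The strongest reply is that Table 6 supports the Section 7 SD. Its conditional power row follows from its mean changes with an SD of about 14.5, so the effect size row may simply be misprinted and the 90% is untouched. Most of this stands. A reader who sees 18.0 in every column might infer that the trial really has about 75% power. The documents do not support that: nothing names 18 as a planning SD, the 90% reproduces from its own inputs, and two rows of Table 6 agree with 14.6.

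The reply does not fully settle which row is wrong. The printed effect sizes also reproduce the conditional power row if the table was built for about 92 of 154 participants, and the printed increases then give about 90% to 92%. That is not the stated design, but it means the source of the error cannot be identified from the documents.

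A second reply is that Table 6 is only guidance. SAP 8.9 has the unblinded statistician fit the primary model to the first 60 participants, rerun the power in PASS, and increase the sample size only when the result lies between 50% and 90%. That uses observed estimates, so neither 14.6 nor 18 drives the decision. This limits the harm. It also means that a reader should not infer actual type I error inflation. What fails is the printed justification, because at the smallest listed effect size conditional power is 28%.

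Third, the sentence that both scales gave the same power is true. It is uninformative rather than wrong.

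**Conclusion.** The concern holds as an internal inconsistency. SAP 7.0 implies an SD of 14.6 CAPS-5 points (24.8 on CAPS-4), while Table 6 ties its effect sizes to its mean changes by 18.0. At 60 of 100, the printed effect sizes carry conditional power about 24 to 28 points below the printed row, and the claim of more than 50% fails for 0.32 through 0.38. The increase row does not give 90% under either SD. The stated 90% power is not refuted; the 75% is conditional on the sponsor confirming 18 as the CAPS-5 SD.

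Assumptions: the Section 7 means and variances are on the CAPS-4 scale; Table 6 mean changes are in CAPS-5 points, since the interim uses CAPS-5 data; conditional power uses the normal approximation with equal arms. If Table 6 were on CAPS-4, 18.0 would still not match 24.8, and an SD of 18 with the 16.9-point difference would give 99.5% power rather than 75%.

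**What to change.** State one planning difference and one SD in CAPS-5 points, with the scale labelled, in SAP 7.0 and under Table 6. Recompute all four rows of Table 6 from that SD at 60 of 100, then check the sentence on conditional power above 50% against the new table.

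- If 14.6 is kept, the 90% stands. The effect size row becomes about 0.39, 0.42, 0.44, 0.47, 0.49, 0.52, 0.54, and the increase row is recalculated (about 142, 111, 84, 61, 41, 24, 7 for the printed mean changes). Do not simply rescale the mean change row to 4.67 to 6.42: that would leave 52% to 89% beside effects whose conditional power is 28% to 65%.
- Only if the sponsor confirms 18 as the CAPS-5 SD, change the stated power in SAP 7.0, Protocol 14.1 and the synopsis to about 75% (47 per group, 9.94-point difference).
- Either way, do not present the agreement between the two scales as support for the CAPS-5 SD.

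The cost is one recalculated table and some wording. The correction itself adds no participants.

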8.0 Analyses

Every effort will be made to ensure complete, accurate and timely data collection and to avoid missing data, to ensure the completeness of the data which can impact the integrity and accuracy of the final study analysis. The statistical analyses will be reported using summary tables, figures, and data listings. All analyses and tabulations will be performed using SAS® Version 9.4 or higher, and S-PLUS. In general, nominal variables will be described in terms of frequencies and percentages and analyzed using chi square analysis. Ordinal and non-normal continuous variables will be described using sample median and range and analyzed by non-parametric statistical tests. Approximately normal variables will be described using sample mean and standard deviations and analyzed by parametric statistical tests. Except for the primary efficacy analysis, all statistical tests will be two-sided and a difference resulting in a p-value of less than or equal to 0.05 will be considered statistically significant. All p-values will be rounded to and displayed in four decimals. If a p-value less than 0.0001 occurs it will be shown in tables as <0.0001. Data not subject to analysis according to this plan will not appear in any tables or graphs, but will be included in the data listings. Selected results may be presented graphically using standard graphical software.

Post-hoc exploratory analyses not identified in this SAP may be performed to further examine the study data. These analyses will be clearly identified as such in the final clinical study report.

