14.2.1.2 Secondary Outcome

If the primary null hypothesis is rejected, overall change in SDS item scores from Visit 3 (Baseline) to Visit 19 will be analyzed by a Wilcoxon Rank Sum Test. Details of analysis are described in the Statistical Analysis Plan.

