A hierarchical testing strategy will be employed to control for type-I error. That is, the hypothesis for the Key Secondary Endpoint (SDS) will only be tested if the statistical test for the Primary Efficacy comparison rejects the null hypothesis. If the statistical test for the Primary Efficacy comparison does not reject the null hypothesis, the analysis of the Key Secondary Endpoint (SDS) will be exploratory. The treatment comparison will be made at a 2-sided, 0.0499 level of alpha. The key secondary estimator of effects of initially randomized treatments will be the difference between groups in mean change in the SDS summary measure from Baseline to 18 weeks after randomization (Visit 19). Least squares means from a restricted maximum likelihood (REML)-based mixed model for repeated measures (MMRM) will be used to compare treatment groups at Visit 19. SDS data collected after treatment discontinuation will not be included in the de jure estimand. Missing data will not be imputed and will be considered missing at random. The model is specified as follows: Let Y_{ij} be the change in the SDS summary measure from the i th

participant at the j th visit, $i = 1, \dots, n$ and $j = 1, 2, 3$, corresponding to post-baseline visits 8, 13, and 19, respectively. The treatment variable X_i is the randomized treatment of the i th participant. The variables T_1 and T_2 , are variables indicating if the data from that record are from visit 13, or 19, respectively. Covariates included in the MMRM model are the continuous baseline SDS summary measure and the binary variable indicating dissociative subtype at baseline. Investigative site is included as a fixed effect. The regression model is specified as follows:

$$Y_{ij} = \alpha + \beta_1 X_i + \beta_{21} T_1 I(j=2) + \beta_{22} T_2 I(j=3) + \beta_{31} T_1 X_i I(j=2) + \beta_{32} T_2 X_i I(j=3) + \beta_4 \text{Baseline_SDS}_i + \beta_5 \text{DS}_i + \phi \text{Site}_i + \epsilon_{ij},$$

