For Table 6, the conditional power estimates and the numbers to increase the sample size to restore 90% conditional power were calculated in PASS version 14 using the module for two-sample t-tests, which is based on the conditional power definitions from Jennison and Turnbull [7]. Since the minimum effect size for all possible scenarios where the sample size would be increased achieves greater than 50% conditional power for N=60, the type-I error rate is preserved with this administrative sample size re-estimation method [8]. However, the sponsor has chosen to allocate 2% of the alpha (0.0001) for this unblinded administrative interim analysis to account for any possible downward bias in the variance estimate. At the time of the interim analysis, the independent unblinded statistician will fit the cleaned data on the first 60 participants to the primary analysis model to estimate the parameters. These parameter estimates will be input to the PASS 14 Mixed Model Repeated Measures module to re-estimate the power. If the power is less than 90% and more than 50%, the independent statistician will increase the sample size up to the point where the power reaches 90%. These results will be provided by the unblinded independent statistician to the DMC.

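### SAP 8.0 labels every non-primary test with p ≤ 0.05 statistically significant, which conflicts with the SDS rule in SAP 8.7.3 and reaches unadjusted exploratory comparisons

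*SAP*

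**What the plan says.** **General rule.** SAP 8.0 begins its testing convention with "Except for the primary efficacy analysis, all statistical tests will be two-sided" and goes on to say that "a difference resulting in a p-value of less than or equal to 0.05 will be considered statistically significant". The primary analysis is the only exception. The key secondary and the exploratory analyses are not exempted.

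**Primary.** SAP 8.7.1: "The primary treatment comparison will be made at a 2-sided, 0.0499 level of alpha".

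**Key secondary.** SAP 8.7.3 states that "A hierarchical testing strategy will be employed to control for type-I error". SDS is tested only if the primary null is rejected; if it is not, "the analysis of the Key Secondary Endpoint (SDS) will be exploratory". For the level, 8.7.3 says "The treatment comparison will be made at a 2-sided, 0.0499 level of alpha". Protocol 14.2.1.2 has the same gate, with no alpha for SDS: "If the primary null hypothesis is rejected, overall change in SDS item scores from Visit 3 (Baseline) to Visit 19" is the condition and endpoint it sets.

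**Exploratory.** SAP 3.4 lists 18 exploratory objectives, offered in support of the primary objective. Most are worded as assessments of differences between treatment groups. SAP 1.0 defines exploratory analyses as a search for trends that could generate hypotheses, and lets them be either inferential or descriptive. No multiplicity adjustment is given for them.

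**The concern.** One decision threshold, for the only formally gated secondary test, is written two ways. SAP 8.0 says p-values are displayed to four decimals, so an SDS p-value shown as 0.0500 is significant under 8.0 and not significant under 8.7.3.

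The wording also matters when the primary test fails. SDS is then still analysed, as exploratory, and 8.0 has no exception that would withhold the significance label from it. The same sentence covers each exploratory scale comparison that is tested. A report that followed 8.0 literally could describe SDS as statistically significant after a failed primary, or describe chance results among many scales that way, with nothing in the rule to mark them as unadjusted. This is a stated rule that needs correcting, not a gap that needs filling.

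**Working it through.** **1. The plan's own alpha.** SAP 8.9 says "the sponsor has chosen to allocate 2% of the alpha (0.0001) for this unblinded administrative interim analysis". 0.05 − 0.0001 = 0.0499, which reproduces the level in 8.7.1 and 8.7.3. (The 2% description does not match: 0.0001/0.05 = 0.2%. That is a separate matter, and 0.0499 follows from the 0.0001.)

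**2. Size of the SDS threshold conflict.** The two-sided critical value is 1.9608 at 0.0499 and 1.9600 at 0.05. The decisions differ only for 0.0499 < p ≤ 0.05. With the gate kept, familywise error for primary plus SDS is at most 0.0499 if SDS is tested at 0.0499, and at most 0.05 if it is tested at 0.05. SAP 8.9 also says SDS is not evaluated at the interim. The numerical conflict has no material effect.

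**3. SDS labelled significant after a failed primary.** With both nulls true and independent tests, the chance is (1 − 0.0499) × 0.05 = 0.0475, about 4.8%. It falls to about 2.0% at an assumed correlation of 0.9 between the two test statistics. Under 8.7.3 such a result is exploratory, so this is the rate of a misleading label, not of a false confirmatory claim.

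**4. Counting the exploratory between-arm comparisons.**
- SAP 3.4 has 13 between-group objectives: DSP-I, BDI-II, PSQI, CPGS, IASC, TAS-20, SCS, EQ-5D-5L, EAT-26, DUDIT, AUDIT, SRNU and HPQSF.
- Remove PSQI. It is absent from SAP Table 1, from the SAP section 5.0 measures schedule, and from Protocol Tables 4 and 6. That leaves 12.
- Add IPF, which SAP Table 1 lists as a between-group comparison. That gives 13.
- SAP 3.4 specifies IASC subscale scores, and Protocol 7.5.6 gives the IASC seven scales. Counting those separately gives 12 + 7 = 19.
- The four CAPS-5 symptom clusters are left out, because SAP 3.4 describes them as within-participant changes.

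**5. Chance of at least one significant label, all nulls true, each test at 0.05.** For m independent tests the chance is 1 − 0.95^m. For equally correlated normal test statistics with pairwise correlation ρ it is 1 − ∫ φ(u) [Φ((c − √ρ·u)/√(1−ρ)) − Φ((−c − √ρ·u)/√(1−ρ))]^m du, with c = 1.96. The documents give no correlation, so the values of ρ are assumptions.

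| Tests | Independent | ρ = 0.5 | ρ = 0.7 | Expected false positives (0.05·m) |
|---|---|---|---|---|
| 13 | 1 − 0.95^13 = 48.7% | 33.4% | 24.1% | 0.65 |
| 19 | 1 − 0.95^19 = 62.3% | 40.9% | 28.3% | 0.95 |

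**The case against.** The strongest reply is that 8.0 is a paragraph of general conventions and 8.7.3 is the specific rule, so the specific text governs. Most of this stands. A reader might infer that 8.0 removes or overrides the gate. The documents do not support that: 8.0 sets a level and says nothing about the order of testing, while SAP 8.7.3 and Protocol 14.2.1.2 both state the gate outright. However, the SAP gives no rule of precedence, and 8.0 exempts the primary analysis by name without exempting SDS.

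A second reply is that the exploratory analyses are already marked as hypothesis-generating. SAP 8.7 specifies descriptive statistics, and no inferential model is named for most of these scales. It is fair that the plan makes no confirmatory claim for them. A reader might infer that unadjusted exploratory tests break the type I error control claimed in 8.7.3. They do not, because that claim covers only the step from primary to SDS. But SAP 8.7 prescribes the same descriptive statistics for the primary and secondary endpoints, so it does not rule out testing. SAP 1.0 allows exploratory inference, and SAP 8.0 then attaches the label to any such test. Only post-hoc analyses must be flagged as such in the study report.

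A third reply concerns the count. A reader might reach 20 to 24 tests by adding PSQI and the CAPS-5 clusters. PSQI has no scheduled data collection, and the clusters address a different null hypothesis, so neither belongs in a between-arm count. In the other direction, EQ-5D-5L and CPGS are counted once each although they have several scores, so 19 is not a strict maximum.

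**Conclusion.** The point holds as a labelling inconsistency of minor severity. SAP 8.0 and 8.7.3 give different thresholds for SDS. As written, 8.0 would apply a significance label to an SDS result after a failed primary and to unadjusted exploratory results. The type I error of the primary-to-SDS hierarchy is not materially affected.

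For the exploratory comparisons, the chance of at least one false label is 49% to 62% if the tests are independent and 33% to 41% at ρ = 0.5. These figures assume that every null is true, that each of the 13 to 19 comparisons is tested once at 0.05, and, for the second range, equal pairwise correlation. A higher correlation lowers them. The need to correct the sentence does not depend on the exact count.

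**What to change.** Reword the sentence in SAP 8.0 along these lines: *Claims of statistical significance are confined to the primary efficacy test and, if that test rejects its null hypothesis, to the key secondary SDS test under Section 8.7.3, each at two-sided 0.0499. P-values for all other treatment comparisons are nominal and unadjusted for multiplicity. They are presented with 95% confidence intervals and without a claim of significance.*

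Limit the change to treatment comparisons. SAP 8.7.2 uses 0.05 as a working cut-off for dropping the COVID-19 interaction and for considering additional covariates, and those uses should stay as they are.

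The cost is one amended sentence, with no change to data collection, sample size or power. The downside is that exploratory results can no longer be described as significant.
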